11.2. Type of statistical methods

All primary and secondary endpoints will be summarized and where relevant represented graphically

Primary endpoint:

The change from baseline in PaO₂/FiO₂ ratio will be analyzed using a Mixed Model Repeated Measures (MMRM) analysis with a fixed effect for Baseline PaO₂/FiO₂ ratio, treatment, day and treatment by day interaction, where day is categorical. Subject will be fitted as a random effect and an unstructured covariance will be used unless it fails to converge, where other covariance structures will be considered. Other covariates, such as gender, may also be included in the model, if by the time of the analysis these have been identified as key differentiators in terms of COVID-19 recovery. If the variability is shown to be inappropriate for this additive model, then a log transformation of the PaO₂/FiO₂ ratio may be considered.

Data from SOC in another study with a very similar protocol may be incorporated into the analysis using a Bayesian frame work. This will be described more fully in the statistical analysis plan (SAP).

A similar analysis for the P(A-a)O₂ gradient will be completed

Other Endpoints:

Other continuous endpoints will be analyzed in a similar way using an MMRM.

Response rates, such as 28 day all-cause mortality a logistic regression will be used.

Count data will use a generalized linear model with a log link unless the model is either over or under dispersed and then an alternative approach will be used. If it is counts out of a fixed number of days, then a logistic regression will be considered.

For the final follow up, a survival analysis with Kaplan-Meir plots will be created covering from Day 1 to end of follow up.

The detail around the analyses will be explained in more detail in the SAP and as this is an exploratory study, additional analyses may be considered to explore the data more fully.

Interim analyses: will be performed when 42 patients have reached primary endpoint analysis.

After half the patients have completed day 15 an interim analysis will be completed to understand if there is already enough evidence to prompt further work on COVID-19 treatment with Zilucoplan®. There is no plan to stop the study at this stage.

Analyses will also be completed when all patients have finished day 28 to assess all pre-follow up assessments and 28 day mortality (via phone call). This will enable key results to be understood as soon as possible without compromising the study.

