3 DATA ANALYSIS CONSIDERATIONS

3.1 General presentation of summaries and analyses

Statistical analysis and generation of tables, figures, participant data listings, and statistical output will be performed using SAS Version 9.1 or higher.

Descriptive statistics will be displayed to provide an overview of the study results. For categorical parameters, the number and percentage of participants in each category will be presented. The denominator for percentages will be based on the number of participants appropriate for the purpose of analysis. Unless otherwise noted, all percentages will be displayed to 1 decimal place. No percentage will be displayed for zero counts, and no decimal will be presented when the percentage is 100%. For continuous parameters, descriptive statistics will include number of participants with available measurements (n), mean, standard deviation (SD), median, minimum, and maximum.

Decimal places for descriptive statistics will always apply the following rules:

- “n” will be an integer.
- Mean, SD, and median will use 1 additional decimal place compared to the original data.
- Coefficient of variance (CV[%]) will be presented with 1 decimal place.
- Minimum and maximum will have the same number of decimal places as the original value.

Statistical tests of the primary efficacy endpoints will be presented as 2-sided p-values rounded to 4 decimal places. P-values less than 0.0001 will be presented as “<0.0001” and p-values greater than 0.9999 will be presented as “>0.9999.” Appropriate statistical models will be fit to the various data collected for the secondary objectives, as described in their respective sub-sections in Section 8 for the purposes of estimation. No p-values will be provided for the analysis of endpoints associated with the secondary objectives, rather 95% confidence limits of the results of various comparisons of interest will be provided.

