
Objective 2 Percentage of participants not deteriorating according to the ordinal scale by 1 point between D1 and D6, between D7 and D15 and between D16 and D28 – not deteriorating corresponds to Stable + Responders
	
A participant is classified as Stable + Response if at no time CFB < -1. Create indicator variable (3 levels) if the relative day of START of Stable or Response falls between D1 and D6, between D7 and D15 and between D16 and D28 for each participant
	
Frequency table and percentage responders in each of the categories defined by the indicator variable, by treatment. Exact 95% confidence intervals for each percentage

Objective 2 6-point ordinal Scale at D6 and D15 and D28 in relation to D-Dimers and complement C5a levels at baseline
		
Box-whisker plot of baseline D-Dimers and complement C5a for each score (x-axis) reported on each of D6, D15 and D28

Objective 2 Change from baseline in SOFA score (https://www.mdcalc.com/sequential-organ-failure-assessment-sofa-score)
	
Change from baseline to D6 and D15 in SOFA score
	
Summary statistics for raw data and change from baseline

Endpoint	Derivation	Analysis
to Day 6, Day 15 (or at discharge, whichever comes first)		

Objective 2
 
Number of days with fever (defined as 37.1°C or more) during 28-day assessment period
	
Create indicator variable for each participant on each day where temperature is above 37.1 °C
 
Create variable with total number of days where temperature was above 37.1 °C for each participant
 
Create variable for each participant giving total number of days where temperature was recorded
	
Summary statistics to provide n, average number of days, SD, median, minimum and maximum where temperature was above 37.1 °C by treatment
 
Produce line plot of temperature over time for each patient together with average line per treatment group.
 
Temperatures are due to be taken daily until discharge – indicate the number of subjects on each day in each treatment arm

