
Objective 2
 
Time since randomization until absence of LAST fever (defined as 37.1°C or more) for more than 48 h without antipyretics (use last fever to account for possibility that participants have intermittent fever per this definition)
	
Antipyretic use in last 24 hours is collected on eCRF on every day. Use highest temperature recorded in last 24 hours, not the 7-10am temperature to identify the date when the last fever ended per definition.
 
Create variable which contains number of days between this date and date of randomisation for each participant. If a participant has had no episodes of the fever, the number of days is 0.
 
Create indicator variable (censor) to indicate if participant has recovered from the last fever at time of analysis (0=recovered, 1=fever is ongoing at time of analysis). If a participant has had no fever, (i.e. time=0), censor=0.
	
Kaplan-Meier analysis using PROC LIFETEST. Strata ACTARM.
 
Request Failure plot adjusting axis and heading titles to reflect responder and not failure
 
Output statistics:
 
Appropriate statistics from analysis as indicated in mock shell

Endpoint	Derivation	Analysis

Objective 2
 
Duration of hospital stay
 
Duration of hospital stay of survivors
	
Calculate duration of hospital stay in days (Hospital Discharge date-Hospital Admission date)
 
Create indicator variable to flag survivors
	
Summary statistics: n, nmissing, mean, SD, median, minimum, maximum
 
By treatment arm

Objective 2
 
Number of days requiring supplemental oxygenation after randomisation to Day 28 (or discharge, whichever comes earlier)
	
Number of days where Suppl O₂ = ‘Y’ from Vital parameters
	
Summary statistics: n, nmissing, mean, SD, median, minimum, maximum
 
By treatment arm

Objective 2
 
Time since randomization until improvement in oxygenation (defined as independence from supplemental oxygen) during 28 day assessment period (or discharge, whichever comes earlier)
	
Independence from supplementary oxygen means no further ‘Y’ after a ‘N’
	
Kaplan-Meier analysis using PROC LIFETEST. Strata ACTARM.
 
Request Failure plot adjusting axis and heading titles to reflect responder and not failure
 
Output statistics:
 
Appropriate statistics from analysis as indicated in mock shell

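### SAP Table 8.1 replaces the protocol's models for SOFA change, oxygen days and fever days with per-arm summaries, and SAP 3.8 does not declare it, so these endpoints get no treatment difference or confidence interval

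*SAP*

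**What the plan says.** Protocol 4.2 lists change in SOFA score to D6 and D15, days on supplemental oxygen, and days with fever as secondary endpoints. Protocol 11.2 assigns methods by data type:

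- Continuous: "Other continuous endpoints will be analyzed in a similar way using an MMRM".
- Counts: "Count data will use a generalized linear model with a log link unless the model is either over or under dispersed", in which case another approach is used.
- Bounded counts: "If it is counts out of a fixed number of days, then a logistic regression will be considered".

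SAP Table 8.1 (section 8.2) plans the following:

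- SOFA change: "Summary statistics for raw data and change from baseline".
- Oxygen days: "Summary statistics: n, nmissing, mean, SD, median, minimum, maximum", by arm.
- Fever days: the same kind of descriptive statistics by arm, with line plots of temperature. The derivation column adds "Create variable for each participant giving total number of days where temperature was recorded", but the analysis column does not mention that variable.

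SAP 3.1 says that models will be fitted for the secondary objectives for estimation, as set out in Section 8. It replaces p-values: "rather 95% confidence limits of the results of various comparisons of interest will be provided". SAP 3.8 declares three changes from the protocol: a baseline-by-day term, windowed nominal days, and mapping of the discharge-day result. None concerns these endpoints.

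**The concern.** Going from a named model to a table of arm means changes the planned analysis, and SAP 3.8 is where a reader would look for such a change. The secondary objective on clinical outcome names SOFA score and supplemental oxygen use, and fever days bear on its defervescence component. Confidence limits are the only inferential output that the SAP plans for secondary endpoints, so a row without a model has none. In a 2:1 trial of 81 patients, two arm means printed side by side invite a reading that the data may not support. If someone then computes a difference after seeing the data, the choice of model, adjustment and handling of deaths will not have been fixed in advance.

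**Working it through.** **Comparison of the texts**

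| Endpoint (protocol 4.2) | Protocol 11.2 | SAP Table 8.1 | Declared in SAP 3.8 |
|---|---|---|---|
| SOFA change | MMRM | Descriptive | No |
| Oxygen days | Log-link GLM, an alternative, or logistic | Descriptive | No |
| Fever days | Log-link GLM, an alternative, or logistic | Descriptive | No |

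SAP 8.2 itself classes changes from baseline and numbers of days as continuous data. Under either document's classification, protocol 11.2 calls for a model. Elsewhere in Table 8.1 models are specified: an MMRM for ordinal-scale change, an analysis of variance with a baseline covariate for AUEC over time, and logistic regression with an odds ratio and 95% CI for mortality.

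**Sample size inputs.** Protocol 11.1 gives 54 and 27 patients, a difference of 80, an SD of 105, two-sided 5%, dropout below 10%, and power above 85%. The plan's figure reproduces:

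- SE = 105 × sqrt(1/54 + 1/27) = 105 × 0.2357 = 24.75. 80/24.75 = 3.23, and the normal-approximation power is 89.8% (t-based 89.1%).
- With 10% dropout (48.6 and 24.3): SE = 105 × 0.2485 = 26.09. Power is 86.6% (t-based 85.7%).

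**Width of the missing interval.** For any difference in means, in units of the outcome's SD and unadjusted for baseline:

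- Half-width = 1.96 × sqrt(1/54 + 1/27) = 0.46 SD (0.47 with t).
- After 10% dropout: 1.96 × 0.2485 = 0.49 SD (0.50 with t).

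The documents give no SD for SOFA, oxygen days or fever days, so this cannot be turned into score points or days.

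**Why recorded days should not be the offset.** Temperature is recorded daily until discharge, so the number of recorded days is itself an outcome that treatment may shorten. As a hypothetical case, take control patients with 10 oxygen days in 12 recorded days and treated patients with 5 in 6:

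- Rate ratio with the offset: (5/6)/(10/12) = 1.0.
- Ratio over a fixed 28 days: (5/28)/(10/28) = 0.5.

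The offset removes a halving of oxygen days. Deaths act in the other direction on the raw count: a patient who dies early contributes few oxygen or fever days and looks like a good outcome.

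**The case against.** The strongest defence is that this is a proof-of-concept trial. SAP 4.5 calls the secondary hypotheses exploratory, no secondary p-values are planned, and the protocol defers: "The detail around the analyses will be explained in more detail in the SAP". That limits the seriousness but does not remove the point. The protocol defers detail after naming a model, and dropping the model is more than detail. The SAP 8.2 fallback to summaries applies only if the data prove unsuitable for modelling, whereas here no model is planned.

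Other parts of the defence stand, and several stronger readings should be resisted:

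- A reader might infer that fever and oxygen are left with arm means alone. They are not. Table 8.1 has Kaplan-Meier rows by arm for time to the end of the last fever and time to independence from oxygen. Protocol 4.3 lists both as exploratory.
- A reader might take SAP 3.1 as a promise of an interval for every row. It refers to comparisons of interest and points to Section 8, so the conflict is one of stated intent.
- A reader might blame the SAP for letting length of stay into oxygen days. The protocol's own definition ends that count at discharge.
- A reader might say that the recorded-days variable is never used. The table shells, which SAP 8.2 cites for further detail, were not available to check.
- A reader might put a figure on the precision lost by not adjusting SOFA for baseline. That needs a correlation that the documents do not give and assumes equal variances. It would also compare against an unadjusted SOFA test that the SAP does not plan.

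The plots in SAP Section 8 may carry 95% CIs for means, and n, mean and SD by arm allow a crude difference to be worked out by hand. Neither is a planned estimate of the treatment effect.

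**Conclusion.** The point holds as a discrepancy that should be corrected. For three secondary endpoints the SAP drops the protocol's model without declaring it and plans no between-arm estimate or 95% CI. What is lost is estimation, not a confirmatory test, and the primary result is untouched. The unreported uncertainty is about 0.46 to 0.50 SD either side of a difference in means, assuming 54 and 27 patients, up to 10% dropout and no baseline adjustment.

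Two limits apply. The SAP cites protocol 3.0, whose section 11.2 is not available. The change log's entries for that section record only a clarification about which endpoints are summarised and the Bayesian wording, so nothing suggests that the models came later. For counts the protocol leaves a choice of method, but the methods it names are models.

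The three endpoints are not a complete list of such gaps. The 6-minute walk row has an empty analysis cell, and nosocomial infection has procalcitonin summaries but no between-arm analysis of incidence.

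**What to change.** In SAP Table 8.1:

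1. **SOFA change.** Use the MMRM already written for ordinal-scale change (baseline, treatment, nominal day, baseline by day, treatment by day). Report the difference and 95% CI at D6 and D15.
2. **Oxygen days and fever days.** Name one model in advance: the protocol's count model, or a quasi-binomial model over a fixed 28-day denominator. These estimate different ratios, so they are not interchangeable. Do not use recorded in-hospital days as an offset. Report the between-arm ratio and 95% CI. State that days after discharge count as zero, and state how deaths are handled.
3. **Covariate.** Baseline ordinal score may be added to the count models as an option. It is not in the protocol and should be labelled as an addition.
4. **Records.** Keep the descriptive tables. Enter any remaining departure from protocol 11.2 in SAP 3.8 with a reason. If the sponsor prefers to stay descriptive for any of these endpoints, say so there and align SAP 3.1.

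The cost is SAP wording and three model fits on data already collected.

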4.2. Secondary End Points + Time Points

-To study if early intervention with Zilucoplan® is safe (number of AEs/SAEs)

-To study if early intervention with Zilucoplan® affects clinical outcome

defined by 6-point ordinal scale change between day 1 and respectively day 6, day 15 (or discharge, whichever comes first) and day 28 (by phone call). 6-point ordinal scale defined as

1. Death
2. Hospitalized, on invasive mechanical ventilation or ECMO;
3. Hospitalized, on non-invasive ventilation or high flow oxygen devices;
4. Hospitalized, requiring supplemental oxygen
5. Hospitalized, not requiring supplemental oxygen

Not hospitalized

-Number of days requiring supplemental oxygen after randomization to Day 28 (or discharge, whichever comes first)

-Number of days with fever (defined as 37.1°C or more) during 28-day assessment period

- change from baseline in SOFA score to D6, D15 (or on discharge, whichever is first)

- Time to at least a 2-point improvement or discharge sustained up to D28 on the 6-point ordinal scale during 28-day assessment period

-Incidence of nosocomial bacterial or invasive fungal infection during 28-day assessment period

Patients with viral respiratory infection are at risk of secondary bacterial infections. As part of routine clinical care, sputum or BAL samples will be collected in patients suspected of secondary bacterial

pneumonia, and checked for the presence of bacteria. Measurements of procalcitonin levels will be performed at least three times per week until day 14 or hospital discharge.

- **All-cause mortality rate at 28 days post randomization (all treated participants)**
- All-cause mortality rate at 28 days post randomization (excluding participants that required invasive mechanical ventilation or ECMO, non-invasive mechanical ventilation or high-flow oxygen devices within 24 hours prior to or after randomization)**
- All-cause mortality rate at 28 days post randomization (excluding participants that required invasive mechanical ventilation or ECMO within 24 hours prior to or after randomization)**
- All-cause mortality rate at 28 days post randomization (only including patients that required invasive mechanical ventilation or ECMO within 24 hours prior to or after randomization)**
- Incidence of patients in each category of the 6-point Ordinal Scale at follow up 12-22 weeks post-randomization**
- All cause mortality at follow up 12-22 weeks post-randomization for all treated participants**

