Secondary Objective	Endpoint	Measurement

1)continued: To study if early intervention with Zilucoplan® affects clinical outcome defined by duration of hospital stay, 6-point ordinal scale, time to defervescence, supplemental oxygen use, SOFA score
	
Number of days with fever (defined as 37.1°C or more) during 28-day assessment period
 
Time since randomization until absence of LAST fever (defined as 37. 1°C or more) for more than 48 h without antipyretics (use last fever to account for possibility that participants have intermittent fever per this definition)
	
Temperature Vital Parameters
 
Antipyretic use in last 24 hours is collected on eCRF on every day. Use highest temperature recorded in last 24 hours, not the 7-10am temperature

	
Duration of hospital stay
	
From DATES eCRF

	
Duration of hospital stay of survivors
	
From DATES

	
Number of days requiring supplemental oxygenation after randomisation to Day 28 (or discharge, whichever comes earlier)
 
Time since randomization until improvement in oxygenation (defined as independence from supplemental oxygen) during 28-day assessment period (or discharge, whichever comes earlier)
	
Number of days where Suppl O₂ = ‘Y’ from Vital parameters
 
Independence from supplementary oxygen means nor further ‘Y’ after a ‘N’

	
Number of days with hypoxia (defined as SpO₂ <93% breathing room air or the dependence on supplemental oxygen after randomisation to Day 28 (or discharge, whichever comes earlier)
	
Use SpO₂ (%) and Supple O₂ (Y/N) from Vital parameters

Secondary Objective	Endpoint	Measurement

2) To study if early intervention with Zilucoplan® affects progression to mechanical ventilation and/or ARDS
 
And
 
Duration of ICU stay
	
Duration of ventilator free days after randomisation to Day 28 (or discharge, whichever comes earlier)
 
Duration of invasive mechanical (including ECMO) and non-invasive mechanical ventilation in ventilated participants
	
Use data from Vital parameters (include all days, where NIV, IV and ECMO='N')
 
Complement of above (exclude participants who are not ventilated i.e. do not include these with a duration of 0)

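### SAP Table 8.1 counts fever days as strictly above 37.1 °C, although the endpoint is defined in both documents as 37.1 °C or more, so days at exactly 37.1 °C drop out

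*SAP*

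**What the plan says.** **Definition.** Protocol section 4.2 gives the secondary endpoint as "Number of days with fever (defined as 37.1°C or more) during 28-day assessment period". The endpoint list in SAP 2.2.1.2 and the endpoint column of SAP Table 8.1 (section 8.2) use the same inclusive cut-off.

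**Derivation and analysis.** In that same Table 8.1 row, the derivation column has two instructions: "Create indicator variable for each participant on each day where temperature is above" 37.1 °C, and "Create variable with total number of days where temperature was above 37.1 °C for each participant". The analysis column asks for summary statistics ending in "minimum and maximum where temperature was above 37.1 °C by treatment".

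**Neighbouring endpoint.** The next fever row in Table 8.1 is "Time since randomization until absence of LAST fever (defined as 37.1°C or more) for more than 48 h without antipyretics". Its derivation finds the end of the last fever by that definition. The current protocol lists this endpoint as exploratory (section 4.3); the SAP lists it among the secondary endpoints.

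**Which temperature.** Two temperatures are recorded each day, a morning value and the highest in the preceding 24 hours. The measurement column of SAP 2.2.1.2, in a cell that serves both fever endpoints, says "Use highest temperature recorded in last 24 hours, not the 7-10am temperature". The Table 8.1 row for days with fever says only temperature.

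**Inference.** SAP 3.1 states: "No p-values will be provided for the analysis of endpoints associated with the secondary objectives".

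**The concern.** The cells that tell the programmer what to compute do not compute the endpoint named beside them. A day on which the temperature is exactly 37.1 °C satisfies the definition and fails the derivation.

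Two things follow if the derivation is coded as written. First, the reported mean and median number of fever days describe a different quantity from the protocol's secondary endpoint. Second, two fever outputs can disagree about one patient. A participant whose highest temperatures reach 37.1 °C and never exceed it would have zero fever days in one table and a fever to recover from in the next.

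This is not a declared change. SAP 3.8 lists the departures from the protocol's analyses (the baseline-by-day term, nominal-day windows, and mapping of discharge results), and the fever cut-off is not among them.

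**Working it through.** **Step 1. Compare the cut-off wherever it appears.**

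| Place | Cut-off |
|---|---|
| Protocol 4.2, days with fever | ≥ 37.1 °C |
| SAP 2.2.1.2, days with fever | ≥ 37.1 °C |
| SAP Table 8.1, days with fever, endpoint column | ≥ 37.1 °C |
| SAP Table 8.1, same row, daily indicator | > 37.1 °C |
| SAP Table 8.1, same row, day total | > 37.1 °C |
| SAP Table 8.1, same row, summary statistics | > 37.1 °C |
| SAP Table 8.1, time to absence of last fever | ≥ 37.1 °C |

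The mismatch lies within one row, so it is not explained by a difference between protocol and SAP versions.

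**Step 2. Illustrate the size.** The plan has no figure of its own to reproduce here. Everything in this step is assumed: readings rounded to 0.1 °C and normally distributed, with mean m from 36.8 to 38.5 °C and SD s from 0.4 to 0.8 °C. A recorded 37.1 then covers 37.05 to 37.15, so

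- P(reading = 37.1) = Φ((37.15 − m)/s) − Φ((37.05 − m)/s)
- days lost per 14 recorded days = 14 × P(reading = 37.1)
- share of defined fever days lost = P(reading = 37.1) / P(reading ≥ 37.1)

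For m = 37.0 and s = 0.4: Φ(0.375) − Φ(0.125) = 0.096. Before rounding, 14 times this is 1.35 days. P(reading ≥ 37.1) = 1 − Φ(0.125) = 0.450, so the share lost is 21.4%.

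Results over s = 0.4, 0.6 and 0.8:

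| Assumed mean (°C) | Days lost per 14 recorded | Share of fever days lost |
|---|---|---|
| 36.8 | 0.65 to 1.05 | 12.3 to 28.3% |
| 37.0 | 0.69 to 1.35 | 10.4 to 21.4% |
| 37.2 | 0.69 to 1.35 | 8.6 to 14.9% |
| 37.5 | 0.62 to 0.85 | 6.2 to 7.0% |
| 37.8 | 0.30 to 0.48 | 2.2 to 4.1% |
| 38.0 | 0.11 to 0.37 | 0.8 to 3.0% |
| 38.5 | 0.00 to 0.15 | 0.0 to 1.1% |

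The range is about 0 to 1.4 days per 14 recorded. It depends almost entirely on how close the readings lie to the cut-off. A single fixed distribution also ignores defervescence, during which readings would move through the cut-off.

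**Step 3. Effect on the comparison of arms.** Let D_A and D_B be the mean number of days at exactly 37.1 °C in each arm. The exclusive rule lowers the arm means by D_A and D_B, and changes their difference by D_A − D_B. That is zero if the two are equal. The documents give no basis for estimating it.

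**Step 4. Check the temperature source.** SAP 2.2.1.2 requires the 24-hour maximum. The derivation for time to absence of last fever repeats this; the derivation for days with fever does not. SAP 4.3 has a general rule that takes the first value when several are recorded on one day. A programmer working from Table 8.1 alone could therefore use the morning reading.

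**The case against.** The strongest reply is that little depends on this. The endpoint gets summary statistics and a line plot by arm, without p-values. SAP 4.5 calls the secondary hypotheses exploratory, the rule is identical in both arms, and the line plot of raw temperature does not use the cut-off. All of this stands, and it limits the importance of the point.

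A second reply is that the outcome of programming is not known. SAP 8.2 describes Table 8.1 as giving brief details, with more in the mock table shells, which are not part of these documents. The inclusive definition sits in the same row, so a programmer might code it correctly. That is fair. What can be said is that the row contradicts itself and that its derivation, followed literally, gives the wrong count.

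A reader might also infer that 37.1 °C lies in the middle of the readings, so that a large part of the endpoint is lost. The documents do not support this. They give no temperature distribution and no recording precision. The 24-hour maximum would push readings upward, and protocol section 8.1.8 refers to high fever in this phase of illness. With means of 37.8 °C or above, the illustration gives less than half a day per 14. Nor do the documents support a claim that the treatment comparison is biased, since D_A − D_B is unknown.

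The disagreement with the neighbouring endpoint also carries less weight than it might, because the current protocol treats that endpoint as exploratory.

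**Conclusion.** The contradiction is certain, because it can be read directly from one row of SAP Table 8.1 and confirmed against protocol section 4.2. Taken literally, the derivation omits every day at exactly 37.1 °C from an endpoint that includes such days.

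The size is not known. About 0 to 1.4 days per 14 recorded days is an illustration that rests wholly on the assumed normal distribution, means, SDs and recording to 0.1 °C. It concerns the level within an arm, not the difference between arms. The point is minor: one descriptive secondary summary is affected, both arms are treated alike, and the primary analysis is unchanged. It is worth correcting because the instruction is wrong as written and the correction is nearly free.

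**What to change.** In the Table 8.1 row for days with fever, replace the cut-off with 37.1 °C or more in three places: the daily indicator, the day total and the summary statistics. This adopts the definition that both documents already give, and brings the row into line with time to absence of last fever. State in the same derivation cell that the highest temperature in the last 24 hours is used, as SAP 2.2.1.2 requires, and check that the table shells agree.

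The cost is a wording edit to the SAP, with no new data and no new analysis. It should be made before database lock, since SAP 3.8 rules out amending the SAP for changes made after that point.
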